7. STUDY ASSESSMENTS AND PROCEDURES

Every effort will be made to schedule and perform the procedures as closely as possible to the nominal time provided in [Appendix 11](#), giving considerations to appropriate posture conditions, practical restrictions, and the other procedures to be performed at the same timepoint.

At the discretion of the investigator, subjects may be requested to attend unscheduled visits for additional assessments or procedures, including, but not limited to, safety assessments and prescription of rescue medications.

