8.4. Efficacy Analyses

8.4.1. Primary and Secondary Efficacy Analysis

All subjects in the intent-to-treat population will be included in the primary and secondary efficacy analyses. Descriptive summaries will be presented for clinical response, clinical remission, and endoscopic remission rates. The estimate and 95% confidence interval (CI) of clinical response, clinical remission, and endoscopic remission rates at Day 57 will be calculated using the exact binomial method for each treatment. The Fisher's exact test will be used to evaluate any differences between treatments.

Missing data will be deemed as "unresponsive". If any event that was not initially anticipated demands to reconsider data handling, then the method of handling the relevant data will be established in the statistical analysis plan.

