Appendix 11: Schedule of Assessments

	Induction Phase					
	Visit 1	Visit 2	Visit 3	Visit 4	Visit 5	Visit 6 ^a
	Screening ≤28 days prior to Day 1	Baseline Day 1	Day 8 ^b (± 3 d)	Day 29 (± 3 d)	EOT/ET Day 57 (± 3 d)	Follow-up Day 71 (± 7 d)
Informed consent	X					
Inclusion/exclusion	X	P				
Demographics	X					
Medical history	X	P				
Concomitant medication				X		
Subject diary completion			X			
Study drug						
Randomisation		X				
Study drug administration				X		
Compliance review			X	X	X	
Safety						
Follicle-stimulating hormone ^c	X					
Pregnancy test ^d	X	P		X	X	
Viral serology	X ^e					
Clostridium difficile test	X					
Chemistry, haematology, coagulation, and urinalysis	X	P		X	X	X
Vital signs	X	P		X	X	X
12-lead ECGs	X	P		X	X	X
Physical examination	X			X	X	X
Adverse event monitoring				X		
Endoscopic and clinical assessments						
UCEIS	X				X	
Total Mayo score ^f	X				X	
Partial Mayo score ^{f,g}	X	P		X	X	
Modified Mayo score ^{f,h}	X				X	
Health-related quality of life						
IBD questionnaire		P		X	X	
Biomarkers						
C-reactive protein	X	P		X	X	
Faecal calprotectin	X	P		X	X	
Endoscopy/biopsy						
Endoscopy	X ⁱ				X ^j	
Histopathology	X				X	
Tissue concentration					X	

Abbreviations: d = days; ECG = electrocardiogram; EOT = end of treatment; ET = early termination; IBD = inflammatory bowel disease; P = predose; UCEIS = Ulcerative Colitis Endoscopic Index of Severity.

a Only for subjects who do not agree to participate in the extension phase.

b Telephone visit; however, at the discretion of the investigator, subjects may be requested to attend the study site.

c Postmenopausal females only.

d Females of childbearing potential only. A serum pregnancy test will be performed at screening and urine pregnancy tests performed at all other timepoints.

e At a minimum comprises HBV (includes HBV surface antigen, HBV surface antibody, and HBV core antibody), antibodies to hepatitis C virus, and human immunodeficiency virus.

f Mayo scores collected from 1 week prior to each visit (including endoscopy visit).

g Rectal bleeding, stool frequency, and Physician's global assessment.

h Rectal bleeding, stool frequency, and findings on endoscopy.

i Conducted within 7 days of Day 1.

j Endoscopy will be performed ≤7 days prior to the Day 57 visit or on the same day as the other Day 57 procedures/assessments.

	Extension Phase		
	Visit 7	Visit 8	Visit 9
			EOS/ET visit
	Day 71 (\pm 3 d) ^a	Day 85 (\pm 3 d)	Day 112 (\pm 3 d)

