3.2 Secondary Endpoints

The secondary efficacy endpoints are:

- Clinical remission at Day 57, as measured by a total Mayo score of ≤ 2 points, with no individual subscore exceeding 1 point
- Achievement of endoscopic remission at Day 57, as measured by a Mayo endoscopic subscore of 0 or 1.
- Change from baseline to Day 57 in the total Mayo score

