5.2 Handling of Dropouts, Missing Data, and Outliers

For the primary and secondary efficacy responder analysis based on the total Mayo score, subjects with missing data will be deemed as "unresponsive". For subjects who received rescue therapy after the first dose of study drug and prior to Day 57, the response status will be deemed as "unresponsive" regardless of the Mayo score value at Day 57.

In terms of the exploratory endpoints, for the endoscopic response rate by total Mayo score, if a subject has no Mayo endoscopic subscore on Day 57, then the last post-baseline measurement prior to Day 57 will be used and the analysis will be based on the imputed value. If a subject does not have any post-baseline Mayo endoscopic subscore measurement, then the subject will be deemed as "unresponsive".

For modified Mayo remission rate at Day 57, if a subject has more than or equal to 2 questions are not answered, then the subject will be considered as "unresponsive". If a subject has only 1 question is not answered, then the last post-baseline question answered prior to Day 57 will be used to calculate the modified Mayo remission rate at Day 57.

For systemic remission rate at Day 57 based by total Mayo score, if a subject has 2 questions are not answered, then the subject will be considered as "unresponsive". If a subject has only 1 question is not answered, then the last post-baseline question answered prior to Day 57 will be used to calculate the systemic remission rate at Day 57.

For the clinical remission at Day 112, the percentage of subjects with sustained remission on Day 112, and the clinical response rate at Day 112 which are all based on the total Mayo score, if a subject has more than or equal to 3 questions are not answered, then the subject will be considered as "unresponsive". If a subject has less than 3 questions are not answered, then the last post-baseline question(s) answered prior to Day 112 will be used to calculate the total Mayo score and information relevant to derive those Day 112 related exploratory endpoints.

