For the UCEIS exploratory endpoint, if a subject has 1 unanswered UCEIS descriptor for the Day 57 visit, the last post-baseline value for the UCEIS descriptor prior to Day 57 will be used to calculate the final index score and to classify the achievement of endoscopic response by Day 57. If a subject has more than 1 unanswered UCEIS descriptor for the Day 57 visit, the last post-baseline value of the UCEIS index score prior to Day 57 will be used to classify the achievement of endoscopic response by Day 57. If a subject does not have any post-baseline measurement, then the subject will be deemed as "unresponsive".

In terms of handling missing/incomplete IBDQ, the following rule (as shown in the table below) will be followed before any imputation to be taken into a place:

	Number of Missing Values				Comments /Actions
	Subscore 1	Subscore 2	Subscore 3	Subscore 4	
Scenario A	0	0	0	0	You can compute 4 subscores and the full IBDQ

CONFIDENTIAL

Page 10 of 30

Statistical Analysis Plan

Sponsor Name: Bridge Biotherapeutics, Inc.
Sponsor Protocol ID: BBT401-UC-005

Scenario B	1	0	0	0	You can compute both the full IBDQ and the 4 subscores, by replacing the missing value with the average mean (computed on the data available for its own subscore)
Scenario C	1	1	1	1	You can compute both the full IBDQ and the 4 subscores, by replacing the missing values with the average means (each one computed on the data available for its own subscore)
Scenario D	2	0	0	0	You can compute the full IBDQ by replacing the 2 missing values with the average mean (computed on the data available for its own subscore). You can compute only 3 subscores
Scenario E	2	1	0	1	You can compute the full IBDQ by replacing the missing values with the average means (each one computed on the data available for its own subscore). You can compute only 3 subscores
Scenario F	2	1	1	1	You cannot compute the full IBDQ (more than 4 missing values). You can compute only 3 subscores
Scenario G	2	2	0	0	You cannot compute the full IBDQ because in more than one subscore there are 2 missing values (even though the total missing value is not exceeding 4). You can compute only 2 subscores.
Scenario H	0	0	3	0	You cannot compute the full IBDQ because there is one subscore with more than 2 missing values. You can compute only 3 subscores.

If the IBDQ missing value scenario is not covered via the process described above, the last post-baseline measurement will be used and analysis will be based on the imputed value.

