6.6.2 Secondary Efficacy Analysis

Centrally read Mayo endoscopic subscores will be used to evaluate the secondary objectives of the study.

The stool frequency and rectal bleeding subscores will use the average of the last 3 non-missing assessments recorded in the subject diary. If an endoscopy is performed, the average of the last 3 non-missing assessments recorded in the subject diary prior to bowel preparation should be used. If the subscore is not an integer, the subscore should be rounded to the nearest integer. Missing values will be considered as unresponsive as described in Section 5.2.

- **Clinical remission at Day 57, as measured by a total Mayo score of ≤ 2 points, with no individual subscore exceeding 1 point.**

Total Mayo Score will be calculated based on the response achieved from all 4 subscores ranged from 0-3 each out of a total sum of 12.

Subjects who have a sum of total Mayo score ≤ 2 points, with no individual subscore exceeding 1 point at Day 57, will be considered as achieving clinical remission.

The number and proportion of subjects with the 95% confidence interval (CI) of clinical remission rate at Day 57 will be calculated using the exact binomial method for each treatment. The Fisher's exact test will be used to evaluate any differences between treatments at Day 57 will be summarised for the induction phase by treatment group for then ITT Population.

- **Achievement of endoscopic remission at Day 57, as measured by a Mayo endoscopic subscore of 0 or 1.**

The number and proportion of subjects achieving endoscopic remission at Day 57 with the 95% CI will be calculated using the exact binomial method for each treatment. The Fisher's exact test will be used to evaluate any differences between treatments at Day 57 will be summarised for the induction phase by treatment group for the ITT Population.

- **Change from baseline to Day 57 in the Total Mayo score.**

Statistical Analysis Plan

Sponsor Name: Bridge Biotherapeutics, Inc.
Sponsor Protocol ID: BBT401-UC-005

Analysis of covariance (ANCOVA) with change from baseline as the dependent variable and baseline value as the covariate variable will be used to compare the change from baseline to Day 57 in the total Mayo score between each treated group and the placebo group. The 95% CI for the treatment differences in the change from baseline will be calculated, and the p-value will be provided.

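### A missing Day 57 endoscopy is a failure for endoscopic remission, but where an early post-baseline read exists the two exploratory endoscopic response endpoints carry it forward as a Day 57 result

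*SAP*

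**What the plan says.** **Endoscopic remission (secondary).** SAP 3.2 defines it as "Achievement of endoscopic remission at Day 57, as measured by a Mayo endoscopic subscore of 0 or 1". The opening text of SAP 6.6.2 applies to all secondary endpoints: "Missing values will be considered as unresponsive as described in Section 5.2". SAP 5.2 has the matching rule, "For the primary and secondary efficacy responder analysis based on the total Mayo score, subjects with missing data will be deemed as" unresponsive, and Protocol 8.4.1 agrees: "Missing data will be deemed as" unresponsive.

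**Mayo endoscopic response (exploratory, drop of at least 1 grade).** SAP 5.2: "if a subject has no Mayo endoscopic subscore on Day 57, then the last post-baseline measurement prior to Day 57 will be used". With no post-baseline subscore at all, the subject is unresponsive.

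**UCEIS response (exploratory, drop of at least 2 points).** In SAP 5.2, one unread descriptor is filled from its last post-baseline value before Day 57. With more than one unread, "the last post-baseline value of the UCEIS index score prior to Day 57 will be used to classify the achievement of endoscopic response". With no post-baseline measurement, the subject is unresponsive.

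**Modified Mayo remission (exploratory).** Two or more unanswered items make the subject unresponsive. A single unanswered item, which may be the endoscopy, is filled from the last post-baseline answer before Day 57. SAP 5.2 does not say what happens if there is no such answer.

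**Timing.** In the induction phase, Protocol Appendix 11 places endoscopy and UCEIS at screening and at Visit 5 only. Visit 5 serves as end of treatment, early termination and Day 57 together. Its footnote reads: "Endoscopy will be performed ≤7 days prior to the Day 57 visit or on the same day as the other Day 57 procedures/assessments". Protocol 7 adds that "subjects may be requested to attend unscheduled visits for additional assessments or procedures". SAP 5.1 analyses by nominal visit and applies no visit windows.

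**The concern.** Endoscopic remission and Mayo endoscopic response come from the same subscore at the same visit, yet the SAP handles its absence in two ways and gives no reason. Carry-forward usually draws on scheduled interim visits. Here there are none for endoscopy, so the rule reaches only a selected group: subjects who left early or had an extra examination. An early improvement in such a subject would be reported as a Day 57 response although nobody looked at Day 57.

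What is at stake is limited but real. The response and remission rates would rest on different treatment of missing examinations. An arm with more early exits or extra endoscopies could gain responders. SAP 6.6.5 compares both response endpoints by Fisher's exact test with about 12 subjects per arm, where one subject counts for a good deal.

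**Working it through.** The documents give no response rate, dropout rate or power for these endpoints, so there is no planned figure to reproduce.

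**Step 1. What can be carried.** SAP section 5 defines post-baseline as after the first dose, so the screening endoscopy cannot be carried. Scheduled endoscopies after the first dose and before Visit 5: 0. An endoscopy done up to 7 days before the Day 57 visit belongs to Visit 5 by the footnote quoted above, so it is not missing. The visit window is Day 57 ± 3, so an on-schedule read can fall as early as Day 57 − 3 − 7 = Day 47. Two sources remain: unscheduled visits (Protocol 7) and early-termination assessments, which Protocol 4.6 asks sites to attempt.

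**Step 2. The rules side by side**, for a non-rescued subject with a baseline subscore of 3.

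| Situation | Endoscopic remission | Mayo endoscopic response | UCEIS response |
|---|---|---|---|
| No Day 57 endoscopy, no early read | Unresponsive | Unresponsive | Unresponsive |
| No Day 57 endoscopy, unscheduled early read of 1 | Unresponsive | Responder | Responder if the early drop is at least 2 |
| Early-termination read of 1 on Day 20, **not** filed as Visit 5 | Unresponsive | Responder | Responder if the early drop is at least 2 |
| Same read, filed as Visit 5 | In remission | Responder | Responder if the drop is at least 2 |

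The rules agree in row 1 and split in rows 2 and 3. In row 4 the read is not missing and carry-forward does nothing, but a Day 20 examination still counts as Day 57, for remission as well. SAP 5.1 does not settle which of rows 3 and 4 applies.

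**Step 3. Modified Mayo remission.** It has three items: stool frequency, rectal bleeding and endoscopy. The first two are also scored at Day 29, so an earlier answer is normally available; for endoscopy none is scheduled. A subject who has left would normally lack all three items at Day 57 and be unresponsive. The fill for endoscopy therefore matters mainly when the other two items are scored at Day 57 and only the endoscopy is missing.

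**Step 4. Size.** Arm size: 36 / 3 = 12, assuming that all 12 are in the intent-to-treat population. Shift in an arm's rate = carried responders / 12:

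- 0 carried: 0 points
- 1 carried: 1/12 = 8.3 points
- 2 carried: 2/12 = 16.7 points
- 3 carried: 3/12 = 25.0 points

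Not every early read is favourable. If w subjects in an arm have one and a share r of the reads meets the response criterion, the expected shift is w × r / 12. Both inputs are assumptions. For w = 1 it is 2.1 points (r = 0.25) or 4.2 points (r = 0.5); for w = 2, 4.2 or 8.3 points.

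**Step 5. Effect on the test.** Two-sided Fisher's exact test, 12 against 12. The SAP states no significance level; 0.05 is assumed from its 95% intervals.

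| Responders with one carried | p | Without it | p |
|---|---|---|---|
| 5 v 0 | 0.037 | 4 v 0 | 0.093 |
| 7 v 1 | 0.027 | 6 v 1 | 0.069 |
| 8 v 2 | 0.036 | 7 v 2 | 0.089 |

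These pairs were chosen because they straddle 0.05; they show what one subject can do, not what is likely. The exact 95% interval is 15.2% to 72.3% for 5/12 and 9.9% to 65.1% for 4/12, so the estimates are imprecise either way.

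**The case against.** Several points on the other side stand.

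- **The fallback.** A reader might infer that every missing Day 57 endoscopy is filled from an earlier one, so that the endpoints always disagree. SAP 5.2 does not support that: with no post-baseline read, both response endpoints give unresponsive, as remission does. That is the ordinary case. It also covers the one missed endoscopy that the protocol foresees (Protocol 7.5, partial Mayo score collected remotely), unless an extra endoscopy was done earlier.
- **Early-termination reads are on schedule.** It is tempting to say that only off-schedule reads can be carried. Early termination shares the Visit 5 column, so that is too strong.
- **Filing.** If nominal Visit 5 includes early termination, the Day 20 subject is scored alike on all endpoints, and the split is confined to unscheduled endoscopies.
- **Direction.** A reader might infer that carry-forward favours active drug. Nothing in the documents shows this. Subjects examined for cause may be worsening, and similar numbers of carried responders in two arms would leave their difference unchanged. Protocol 5.6 also makes non-responders who worsen and need rescue, and subjects who relapse, treatment failures in the intent-to-treat population, although SAP 5.2 writes its rescue rule only for the primary and secondary endpoints.
- **Status.** The affected endpoints are exploratory, and Protocol 8.4.2 says that no formal hypothesis will be tested on them. SAP 6.6.5 nevertheless specifies Fisher's test for them.

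These points narrow the issue but do not remove it. If early-termination reads are filed as Visit 5, carry-forward is nearly idle and little is lost by deleting it. If they are not, it brings early reads back as Day 57 results. Unscheduled reads are exposed either way. Part of SAP 6.6.3 is redacted, but the section states that its sensitivity rules apply to clinical response and clinical remission, not to these endpoints.

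**Conclusion.** The point holds in a limited form. SAP 5.2 treats a missing Day 57 endoscopy differently for remission and for the two response endpoints only in subjects who have an early post-baseline read. Such a read can come only from an unscheduled endoscopy, or from an early-termination endoscopy not filed as Visit 5. Modified Mayo remission has the same weakness for its endoscopic item, and no stated fallback.

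The size is 8.3 points per carried responder in an arm of 12. The number of such subjects is unknown; at zero, nothing changes. The test results shown assume 12 analysed per arm and a two-sided 0.05 level.

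A reader might go on to infer that the primary or secondary results are biased by this rule. They are not: the carry-forward does not apply to them. The separate silence on filing early-termination reads could reach endoscopic remission, so the correction must cover it. Overall this is a cheap improvement to exploratory analyses and worth making before unblinding.

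**What to change.** In SAP 5.2:

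1. Delete the carry-forward for Mayo endoscopic response, for UCEIS response (including the fill for a single unread descriptor) and for the endoscopic item of modified Mayo remission.
2. Classify a subject without a complete Day 57 endoscopic score as unresponsive on these endpoints, as for endoscopic remission. This also supplies the missing fallback for the endoscopic item of modified Mayo remission.
3. State that an early-termination endoscopy done outside the Day 57 window of Protocol Appendix 11 is not a Day 57 value for endoscopic remission, either response endpoint or modified Mayo remission. Note this as an exception to SAP 5.1, which applies no windows. Without this sentence, deleting the carry-forward would not stop an early exit filed as Visit 5 from counting at Day 57.
4. List early-termination and unscheduled endoscopies separately.

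The cost is SAP wording only. A few early reads would be listed but not counted, and a subject with one unread UCEIS descriptor at Day 57 would count as unresponsive, so response rates may be slightly lower. Item 3 could also lower endoscopic remission if early-termination reads would otherwise have been filed as Visit 5.

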Descriptive statistics on total score and its four aspects: bowel, systemic, emotional, and social function at each scheduled visit as well as change from baseline will be calculated for each phase and by treatment group for the ITT Population.

The following categories with number and percentage of subjects will also be presented for total score at each post-baseline visit:

- change \geq 16 points from baseline
- total score \geq 170

Mixed Model Repeated Measures (MMRM), with repeated change from baseline values as the dependent variable and baseline values as the covariate variable, will be used to compare the change from baseline to Day 29 and 57 in the IBDQ score between treatment and placebo group. The sample SAS code is provided in Appendix 2. The 95% CI for the difference in the change from baseline will be calculated for each treatment, and the p-value will be provided.

Statistical Analysis Plan

Sponsor Name: Bridge Biotherapeutics, Inc.
Sponsor Protocol ID: BBT401-UC-005

The normality assumption will be checked through the Shapiro-Wilk test. If the normality assumption is violated at the 0.01 level of significance, an additional nonparametric analysis [REDACTED] will be used to compare each treated group to the placebo group.

- **Histologic remission using histologic category**

Subjects will be dichotomized as "histological remission" versus "histological non-remission" based on the option recorded on the CRF. Subjects with histologic category recorded as "histologic near remission" and "Other" will be categorised as "histologic non-remission". On the other hand, those recorded with "histologic healing", "histologic remission", "histologic remission without basal plasmacytosis", and "histologic remission without basal plasmacytosis or increased mucosal eosinophils" will be grouped to "histologic remission".

A shift table (i.e., cross-tabulations "histologic remission" and "histologic non-remission" at screening versus Day 57) in a form of 2 x 2 table will be presented for each treatment.

The number and proportion of subjects within each combined category will be summarised by treatment group for the ITT Population.

- **Biomarkers, including C-reactive protein and faecal calprotectin, as measured by change from baseline**

Descriptive statistics on biomarkers at each scheduled visit as well as change from baseline will be calculated for each phase by treatment group for the ITT Population.

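### A missing Day 57 IBDQ total would be filled with the Day 29 total before an MMRM that needs no such filling; this may shift the Day 57 difference and gives a smaller standard error than the observed data would

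*SAP*

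**What the plan says.** SAP section 5.2 handles incomplete IBDQ forms in two steps. A table of Scenarios A to H comes first and "will be followed before any imputation to be taken into a place". It replaces a small number of missing items by the mean of the available items in the same subscore. For Scenarios F to H it says that no full score can be computed; the entry for F reads "You cannot compute the full IBDQ (more than 4 missing values". The second step is a fallback for whatever the table does not cover: "If the IBDQ missing value scenario is not covered via the process described above, the last post-baseline measurement will be used". The same sentence makes the carried value the one that is analysed: "the last post-baseline measurement will be used and analysis will be based on the imputed value".

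SAP section 6.6.5 specifies for the IBDQ a "Mixed Model Repeated Measures (MMRM), with repeated change from baseline values as the dependent variable and baseline values as the covariate variable", used to "compare the change from baseline to Day 29 and 57 in the IBDQ score between treatment and placebo group". On inference it says: "The 95% CI for the difference in the change from baseline will be calculated for each treatment, and the p-value will be provided". It does not say that the model is restricted to observed totals, and it does not refer back to section 5.2. The sample code in SAP Appendix 2 is redacted.

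In the schedule of assessments (protocol Appendix 11), the induction-phase IBDQ is collected before dosing on Day 1, on Day 29, and at the combined Day 57 end-of-treatment and early-termination visit. Day 29 is therefore the only earlier scheduled post-baseline value that can be carried to Day 57.

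**The concern.** An MMRM uses incomplete profiles as they stand. A subject with Day 29 but no Day 57 contributes the Day 29 value, and the model allows for the missing visit under a missing-at-random assumption. Carrying Day 29 forward first removes that feature. It assumes no change after Day 29, enters one measurement at two visits, and leaves the model nothing to treat as missing.

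The SAP does not do this consistently. The partial Mayo score goes into the same kind of model at the same two visits (section 6.6.5), but section 5.2 gives it no carry-forward rule, and missing biomarker values are not imputed. SAP section 6.6.3 names sensitivity analyses only for the primary and first secondary endpoints, so nothing would show how far the IBDQ result depends on the fallback.

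At stake are the estimate, interval and p-value for the Day 57 IBDQ difference. Missingness related to outcome is conceivable. Under protocol section 5.6, some subjects who worsen stop study drug and stay in the study for safety assessments. If such a subject had no Day 57 IBDQ, the fallback would credit the Day 29 score.

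**Working it through.** **Inputs.** From the documents: 12 subjects per arm (SAP section 2.2), post-baseline visits at Days 29 and 57, baseline as covariate. The documents give no SD, effect, visit correlation or missing-data rate for the IBDQ, and no formal sample-size assessment (SAP section 2.3), so there is no figure to reproduce. Assumed for illustration: SD 30 points; visit correlation 0.6, varied from 0.4 to 0.8; 10 to 30% of Day 57 totals missing; several mean trajectories.

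**Step 1: bias.** Let m be the share of Day 57 totals carried forward in an arm and r the arm's mean change from Day 29 to Day 57. If missingness is completely at random,

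bias in the Day 57 difference = −m(drug) × r(drug) + m(placebo) × r(placebo).

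| Assumed mean change at Day 29, then Day 57 | Missing, drug / placebo | Calculation | Bias (points) |
|---|---|---|---|
| Drug +15, +30; placebo +10, +15 (true difference 15) | 10% / 10% | −0.1×15 + 0.1×5 | −1.0 |
| same | 20% / 20% | −0.2×15 + 0.2×5 | −2.0 |
| same | 30% / 30% | −0.3×15 + 0.3×5 | −3.0 |
| same | 30% / 10% | −0.3×15 + 0.1×5 | −4.0 |
| same | 10% / 30% | −0.1×15 + 0.3×5 | 0.0 |
| Both arms +15, +30 (true difference 0) | 10% / 30% | −0.1×15 + 0.3×15 | +3.0 |
| same | 30% / 10% | −0.3×15 + 0.1×15 | −3.0 |
| Both arms flat after Day 29 | any | r = 0 in both arms | 0.0 |

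So the bias can be negative, zero or positive. Simulation agrees: +2.95 for the +3.0 case, and +3.7 when dropout depends on observed values.

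**Step 2: standard error.** One active arm was simulated against placebo, up to 4000 runs per setting, using the first trajectory, correlation 0.6, equal missingness and missing completely at random. The carried-forward data were analysed by baseline-adjusted ANCOVA at Day 57, which is what an unstructured MMRM with a baseline-by-visit term gives on complete data. The comparator was the likelihood estimate from observed totals only.

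| Missing | Carry-forward: mean difference, model SE, sampling SD | Observed totals: mean difference, model SE, sampling SD | Model SE smaller by |
|---|---|---|---|
| 10% | 13.90, 11.37, 11.34 | 14.95, 12.33, 11.95 | 1 − 11.37/12.33 = 8% |
| 20% | 12.72, 11.37, 11.37 | 14.68, 13.05, 12.61 | 1 − 11.37/13.05 = 13% |
| 30% | 11.84, 11.40, 11.58 | 14.84, 14.05, 13.81 | 1 − 11.40/14.05 = 19% |

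With no missing data the SE is about 11.3, so carry-forward reports the precision of a complete trial whatever the missing rate. The model SE for observed totals is an approximation that runs slightly above its own sampling SD. Comparing sampling SDs instead, the gap is 1 − 11.34/11.95 = 5%, 1 − 11.37/12.61 = 10% and 1 − 11.58/13.81 = 16%. At 20% missing, the model-SE gap is 1 − 11.39/13.52 = 16% with correlation 0.4 and 1 − 11.38/12.38 = 8% with correlation 0.8.

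**Step 3: coverage.** Across the settings with 12 per arm, nominal 95% intervals covered 93.9 to 95.5% with carry-forward and 95.5 to 96.5% with observed totals.

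**Step 4: what triggers the fallback.** Scenarios F to H can be read two ways. If they count as covered by the table, a partly completed form that fails the rules stays missing while a wholly missing form is filled. If they do not, both are filled. If Day 29 is also missing there is nothing to carry, and the SAP is silent.

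**The case against.** A reader might infer that the rule certainly biases the Day 57 difference in favour of the drug, and that its standard error is too small, so that the interval is invalid. The documents do not support that.

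- Bias is conditional. It vanishes under completely random missingness if means are flat after Day 29, or if rises and missing rates match across arms. Where it exists it can go either way, and the documents give neither trajectories nor missing rates. Harm from dropout after worsening is plausible but was not computed.
- The carry-forward SE agrees with that estimator's own sampling SD (11.37 to 11.40 against 11.34 to 11.58), and coverage at 12 per arm is close to nominal. It is smaller than the SE from observed totals, not too small for its own estimator.
- In the simulated case above, total error at this sample size favours carry-forward. Root-mean-square error, from bias and sampling SD, is √(1.10² + 11.34²) = 11.4, √(2.28² + 11.37²) = 11.6 and √(3.16² + 11.58²) = 12.0. For observed totals it is 12.0, 12.6 and 13.8.
- Exposure is probably limited. The fallback follows the item rules, Scenarios F to H may already be left missing, and the Day 57 column is also the early-termination visit, so some early leavers will supply a total.
- The endpoint is exploratory, and protocol section 8.4.2 plans descriptive summaries with no formal test.
- With the code redacted and no cross-reference between the two sections, entry of carried values into the MMRM is the plain reading but is not confirmed.
- An MMRM is not immune to missingness that depends on unobserved values.

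All of this stands, and it limits the size of the point. It does not justify the rule. The lower total error comes from the no-change assumption, for which the SAP gives no reason. The SAP has also gone beyond the protocol by attaching an interval and p-value, so the basis for them should be clear.

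**Conclusion.** The point holds in limited form and is minor. As written, the SAP fills uncovered missing IBDQ totals by carry-forward and bases the analysis on them. It then specifies a model that needs no filling. On the plain reading, this replaces missing-at-random handling with an assumption of no change after Day 29.

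The Day 57 difference may move in either direction, by zero to about 4 points in the illustrations, against an SE of about 11 to 14. The model SE is about 8 to 19% smaller than that of an observed-data MMRM at 10 to 30% missing. These figures rest on assumed SD, correlation, trajectories and missing rates; the SE range also assumes completely random missingness. A claim of certain bias, or of an SE too small for the estimator used, would go beyond the evidence. The ambiguity over Scenarios F to H is a separate drafting gap in the same sentence and does not depend on these assumptions.

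**What to change.** In SAP section 5.2, keep the item-level rules in Scenarios A to H. State that totals that cannot be computed, including Scenarios F to H and wholly missing forms, stay missing in the MMRM. In section 6.6.5, state that the IBDQ model runs on observed totals, meaning those obtained directly or through the item rules. Delete the carry-forward sentence, or keep it only to define a labelled sensitivity analysis.

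The same edit should say how a missing total counts in the two IBDQ categories in section 6.6.5 (change of at least 16 points, total of at least 170), since these also use the total.

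The cost is a reworded sentence or two, with no new data and no change to conduct. The Day 57 interval will be somewhat wider if totals are missing.
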